Subject Participation Duration	Phase I (Randomized, Blinded): 6-8 weeks (Active rTMS vs. Sham) Phase II (Non-Randomized, Open-label): Acute Treatment (Arm 1) vs. Maintenance Treatment (Arm 2) Arm 1: 6-8 weeks of open-label acute treatment (for Phase I treatment nonresponders) Arm 2: 12 months of open-label, bi-weekly maintenance treatment (for Phase I treatment responders)
Objectives	1) To evaluate the antidepressant effects of daily, active rTMS (when compared with sham treatment) in adolescents meeting criteria for Major Depressive Disorder, single or recurrent episode (Phase I). 2a) To evaluate the benefit of daily, active, open-label rTMS in Phase I nonresponders (Phase II, Arm 1). 2b) To evaluate the benefits of bi-weekly, active, open-label maintenance rTMS treatment for Phase I responders over the course of 12 months post-acute treatment (Phase II, Arm 2). 3*) To evaluate, by proton magnetic resonance spectroscopy (¹ H-MRS) at 3 Tesla (3T), neurometabolic biomarkers at the beginning and end of each study phase. 3a. Define regional specificity [anterior cingulate (AC) and left dorsolateral prefrontal cortex (L-DLPFC)] of cerebral metabolites (i.e. glutamate and glutamine) in adolescent depression. 3b. Study whether specific neurochemical resonances are associated with response, remission, and/or maintenance of improvement of clinical depressive symptoms when rTMS is used to treat adolescent depression.
	*Assessed at MCR site only
Number of Subjects	Phase I: Total of 75 enrolled (38 Active/37 Sham) across both sites (50 at MCR; 25 at MUSC) Phase II: All treatment responders and nonresponders will be offered qualified follow-up treatments based on Phase I outcomes.
Diagnosis and Main Inclusion Criteria	Diagnosis of Major Depressive Disorder, single or recurrent, antidepressant treatment-resistant
Study Device	NeuroStar™ TMS System in XPLOR® research configuration

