3.1 General Design

Treatment-site Localization Procedure:

A neuroradiologist at each site will review baseline MRI for potential exclusionary head and brain pathology. This localization procedure is the same procedure utilized preoperatively for neurosurgery – using a frameless stereotactic system (STEALTH – Mayo; Brainsight – MUSC). The optimal site of treatment, L-DLPFC, operationally defined as the gray matter of the superior frontal sulcus and portions of the superior and middle frontal gyri, containing Brodmann's areas 9 and 46. This location will be designated with a fiducial marker, along with clearly marked anatomic landmarks (nasion line, front and back of the ears) will be transferred to a lycra “swim-cap”. The treatment site noted on the swim cap will then be translated to the NeuroStar machine using a 2-dimensional coil template that will align the coil precisely over the designated treatment site. Once in place, treatment-site coordinates will be loaded into the device database so that subsequent treatments will be identically located. This process will forego the “guesswork” associated with moving the coil 5 or 6 cm anteriorly to the optimal motor threshold site – also known as the point at which the contralateral abductor pollicis brevis is consistently stimulated.

Phase I (Randomized, Double-Blinded):

Active Treatment

Adolescents randomized to active rTMS treatments will receive therapy using parameters that have been safely and feasibly utilized in adult randomized, controlled trials [7, 8] and the 2011 Wall et al. open-label trial in adolescents.[1] Stimulation will occur at 120% magnetic field intensity relative to the participant's resting motor threshold, at 10 pulses per second (10 Hz) for 4 seconds, with an intertrain interval of 26 seconds. During the treatment, intensity can be reduced, as needed, to 80% for tolerability. Titration and a return to maximum intensity (not to exceed 120% MT) will occur as tolerated by each participant. This is not expected to impact treatment response but may make the treatment experience more comfortable. Treatment sessions will last for 37.5 minutes (75 trains) to provide a total of 3,000 pulses per treatment session. A total of 30 treatments will be completed within 6-8 weeks of treatment initiation.

Sham Treatment

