5.2 Method for Assigning Subjects to Treatment Groups

Enrolled subjects will be assigned to either the blinded sham coil or the blinded active coil during Phase I of the study using a permuted block randomization method, with the result of the same number of subjects being assigned to both treatment groups. The randomization schedule will be generated by the Mayo Clinic Health Sciences Research (HSR) Biostatistical team. Once generated, the randomization assignment for each subject receiving treatment will be printed on a separate card and sealed in an envelope prepared by the HSR team. These envelopes will be unsealed and subjects will be randomized to the study prior to their first treatment, but not before informed consent/assent has been obtained, they are confirmed to be eligible for the study, and all baseline visit requirements have been fulfilled. In this way, selection bias can be avoided should study staff deduce the nature of the blinded coils. For safety precautions, the full randomization schedule will be sent to the chair of the Data Safety Monitoring Board by the HSR team. In addition, study staff will keep a spreadsheet of the subject number associated with each randomization number, so that the DSMB may unblind a specific subject in the event of a medical emergency.

The XPLOR software has built-in checks that, once a subject has been randomized to a particular coil, will prevent treatment from taking place with the incorrect blinded coil. This safety precaution provides blinding to the staff applying study treatment, staff performing the mood, cognitive, safety, and imaging assessments, and to the subjects – essentially creating a triple-blinded procedure.

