7.2 Statistical Methods

Descriptive Statistics

Univariate descriptive statistics and frequency distributions will be calculated as appropriate for all variables. Baseline values for demographic, clinical, and outcome variables (primary and secondary) will be tabulated for the treatment groups. These analyses will help identify potential confounding variables to be used as covariates in sensitivity analyses. Distributions across subgroups used in randomization will be compared to assess whether the randomization was successful in equalizing distributions of these prognostic variables across treatment groups.

Statistically significant differences on overall comparisons will be explored using multiple pairwise comparisons of each of the (treatment) groups using Bonferroni correction for multiple comparisons. Mean scores and standard deviation for each group will be calculated.

Subsequent multiple comparisons via Tukey's procedure will be set at 0.01 to control Type I error rate.

Primary Hypotheses:

- 1) Adolescents in Phase I treated with active rTMS at the left dorsolateral prefrontal cortex (L-DLPFC) will have significant mood improvement when compared to sham treatment.
- 2) Adolescents in Phase II treated with maintenance rTMS at the L-DLPFC will achieve sustained response of the depressive symptoms.

Phase II represents a proof of concept/preliminary study of long-term maintenance for treatment responders (either active or sham in Phase I) and an opportunity for open-active treatment in nonresponders. The inclusion of phase II is ethically necessary to ensure that all pediatric participants are offered an opportunity to receive active treatment if unresponsive in phase I. The analysis of data collected as part of phase II is exploratory and will include primarily descriptive statistics.

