Treatment outcomes for both phases will be defined as response (CDRS-R raw score <28 & CGI-I ≤2 & CGI-S ≤2), or nonresponse (CDRS-R raw score ≥28 and CGI-I ≥3) assessed using a logistic regression model with independent variables of treatment number (i.e. #10 vs. #20 vs. #30) and gender (male vs. female) will be analyzed. Assessing potential gender effects will be a secondary analysis. The primary analysis will not adjust for gender. Although we anticipate that more females than males will participate in the study, we assume that the distribution of gender will be similar between treatment arms and have no a priori reason to suspect that the efficacy of treatment will be gender specific.

Serious adverse events will be reported as noted within the application. All adverse events will be summarized according to treatment groups. Given the sample size for the current study, the statistical power for detecting differences between groups is limited. However, we will compare between groups using an exact test.

All statistical tests will be performed at the 0.05 significance level.

Secondary Hypotheses (for MCR site only):

Baseline glutamate, reported as a CSF-corrected absolute concentration and as an overlapping resonance with glutamine, will be significantly higher in both AC and L-DLPFC in depressed adolescents as measured by ^1H -MRS at 3T when compared to data derived from previously scanned healthy controls.

In comparison to non-remission subjects, depressed adolescents treated with rTMS who achieve remission (defined as a CDRS-R raw score <28 and CGI-I ≤ 2 and CGI-S ≤ 2 at treatment completion) will exhibit a greater decrease in glutamine, reported as a CSF-corrected absolute concentration percent change (baseline to endpoint) in AC and L-DLPFC as measured by ^1H -MRS at 3T.

The hypotheses will be tested using t-tests. Additionally, analyses of covariance will be performed to control for potentially important covariates or confounders, such as age or gender. Non-parametric distribution will be analyzed by non-ANOVA statistics.

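### Section 5.2 names no stratification factor although 7.2 presupposes one, and the primary active-versus-sham comparison prespecifies no site or baseline CDRS-R term

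*Combined protocol and SAP*

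**What the plan says.** **Allocation.** Section 5.2 describes assignment "using a permuted block randomization method", intended to give equal numbers in the two arms. Each assignment is "printed on a separate card and sealed in an envelope prepared by the HSR team". The section does not say whether the sites draw from separate lists, and it gives no block size and no stratification factor.

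**Balance check.** Section 7.2 nevertheless states: "Distributions across subgroups used in randomization will be compared to assess whether the randomization was successful". It treats these subgroups as prognostic, but no section names them.

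**Software.** Appendix O describes a randomisation module that can balance on site. The protocol does not say that this trial uses it, and it does not match the envelope method of 5.2.

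**Sites.** The Study Summary gives "Total of 75 enrolled (38 Active/37 Sham) across both sites (50 at MCR; 25 at MUSC". Section 3.1 has the sites localising the target with different equipment, "using a frameless stereotactic system (STEALTH – Mayo; Brainsight – MUSC".

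**Primary analysis.** Section 7.2 specifies a "logistic regression model with independent variables of treatment number (i.e. #10 vs. #20 vs. #30) and gender (male vs. female"). It then makes gender a secondary matter and leaves it out of the primary analysis. Neither site nor baseline CDRS-R appears. Analysis of covariance is planned only for the spectroscopy hypotheses at MCR. In section 7.1 the continuous outcome is raw change in CDRS-R, so baseline enters by subtraction only.

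**Sensitivity covariates.** Of the baseline tabulation by treatment group, 7.2 says: "These analyses will help identify potential confounding variables to be used as covariates in sensitivity analyses".

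**The concern.** Three things are left open.

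1. A reader cannot tell what was balanced by design. If the list is common to both sites, balance within site is left to chance. If the list is stratified, as 7.2 implies, the stratification factor is missing from the primary analysis.
2. Two variables that the trial already collects, and that plausibly predict outcome, are not used. The sites differ in size, localisation equipment and population. Baseline severity matters through the endpoint's own definition: entry needs a CDRS-R of at least 40 (section 4.1), while response needs a score below 28 (section 7.2). A subject who enters at 40 must fall 13 points to reach 27; one who enters at 60 must fall 33.
3. The adjusted analyses that should test robustness have no fixed covariates. They are to be suggested by a table by arm, and section 5.7 puts unblinding after all subjects have finished both phases, so outcomes will by then be in hand. This weakens what a supportive sensitivity analysis can show.

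At stake are some precision in the continuous comparison and the credibility of the adjusted results. The validity of the main test is not in question.

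**Working it through.** **Step 1. The plan's own power figures (section 7.1).** Inputs: two-sided alpha 0.05; 65% versus 25%; difference 8.0 with SD 10.0; 35 per group, or 25 per group for completers.

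- Binary, pooled-variance z test, 35 per group: (0.40 − 1.96·√(2·0.45·0.55/35)) / √((0.65·0.35 + 0.25·0.75)/35) = 0.167/0.109 = 1.53, so power is 93.7% (stated 94%). At 25 per group it is 83.2% (stated 83%).
- Continuous, noncentral t: noncentrality 8/(10·√(2/35)) = 3.35 on 68 df gives 91.0% (stated 91%). At 25 per group, 2.83 on 48 df gives 79.1%. The normal approximation gives 91.7% and 80.7% (stated 80% at 25 per group).

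All four figures reproduce, and all come from unadjusted two-group formulas.

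**Step 2. Adjusting change for baseline.** Let r be the baseline-endpoint correlation and k the baseline SD divided by the endpoint SD. In units of the endpoint variance, the change score has variance 1 + k² − 2kr and the ANCOVA residual has variance 1 − r². The ratio is

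(1 − r²) / (1 + k² − 2kr).

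It never exceeds 1, because the denominator minus the numerator is (k − r)². It equals 1 when r = k. The documents give neither r nor k, so both are assumptions. Power is from the noncentral t with SD 10·√ratio and one df lost:

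| k | r | ratio | power, 35 per group | power, 25 per group |
|---|---|---|---|---|
| 1.0 | 0.3 | 0.65 | 98.3% | 93.0% |
| 1.0 | 0.5 | 0.75 | 96.8% | 89.2% |
| 1.0 | 0.7 | 0.85 | 94.7% | 85.2% |
| 0.75 | 0.3 | 0.82 | 95.4% | 86.5% |
| 0.75 | 0.5 | 0.92 | 93.0% | 82.2% |
| 0.75 | 0.7 | 1.00 | 91.1% | 79.3% |
| 0.5 | 0.3 | 0.96 | 92.1% | 80.8% |
| 0.5 | 0.5 | 1.00 | 91.0% | 79.1% |
| 0.5 | 0.7 | 0.93 | 92.9% | 82.0% |

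The ranges are 91-98% at 35 per group and 79-93% at 25 per group.

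**Step 3. A site term.** With one third of subjects at MUSC, a between-site difference of D SDs explains (2/9)D² / (1 + (2/9)D²) of the variance. For assumed D of 0.2, 0.5 and 0.8 this is 0.9%, 5.3% and 12.5%, and power at 35 per group is 91.2%, 92.3% and 94.1%. The gain is about 0 to 3 points.

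**Step 4. Site balance, only if one list serves both sites.** With 38 active among 75 and 25 subjects at MUSC, the number active at MUSC is hypergeometric: mean 25·38/75 = 12.7, SD 2.05, 95% range 9 to 17. The chance of 16:9 or worse in either direction is 14.2%; of 17:8 or worse, 5.0%. Simulating a common list in blocks of 4 or 6 gives 14.6% and 14.2% for 16:9 or worse. With a separate list per site and blocks of 4 or 6 (assumed), 24 of the 25 would fall in complete blocks and the split would be 12:13.

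**Step 5. What such a split does.** Assume a 5-point (0.5 SD) site difference. With 16 active and 9 sham at MUSC, the unadjusted estimate shifts by 5·(16/38 − 9/37) = 0.89 points. With 9 active and 16 sham it shifts by 5·(16/37 − 9/38) = 0.98 points the other way. Against the 8-point target that is 11-12%.

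**The case against.** The strongest reply is that the plan is sound as it stands, and much of that is right.

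- **A reader might infer that randomisation is not stratified by site.** The documents do not say so. Section 5.2 is silent, and the reference in 7.2 to subgroups used in randomisation points the other way. What stands is that the factors are undefined.
- **A reader might infer that covariates picked from imbalance drive the main result.** They do not. Section 7.2 confines them to sensitivity analyses. The primary comparison is simply unadjusted, and that is valid under randomisation.
- **A reader might infer that site differences bias the treatment effect.** An uneven split under a common list is chance imbalance, which averages to zero over randomisations, and its size in Step 5 is modest. Section 3.2.1 also plans inter-rater exercises for CDRS-R across sites, which limits one source of site difference.
- **A reader might take the precision gain as assured.** Power of 95-98% at 35 per group and 85-93% at 25 follows only if baseline and endpoint SDs are equal. The entry floor of 40 may narrow the baseline spread, and Step 2 shows that the gain can then be essentially nil.
- **The gain does not carry over to the binary outcome.** Adding covariates to a logistic model changes the target to a conditional odds ratio and does not shrink its standard error in the same way. Stated binary power is already 94%.

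These replies limit the size of the point. They do not supply the missing factor names, or the missing prespecification of site, baseline and sensitivity covariates.

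**Conclusion.** The point holds as a gap in specification with a cheap improvement attached. Sections 5.2 and 7.2 do not agree on whether strata exist, and no section names them. The primary active-versus-sham comparison includes no site or baseline CDRS-R term, and the sensitivity covariates are not fixed in advance.

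On the continuous outcome the benefit of a baseline term lies between nothing and about 7 points of power at 35 per group (91% to 91-98%), and between nothing and about 14 points at 25 per group (79% to 79-93%). This rests on the assumed ranges for r and k. A site term adds 0 to 3 points at 35 per group for assumed site differences of 0.2 to 0.8 SD. The 14% chance of a 16:9 or worse split applies only if the list is common to both sites, which the documents do not establish. No power gain is claimed for the logistic analysis.

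**What to change.** - **Section 5.2:** state separate permuted-block lists for each site, describe the block scheme, and name any other factor used, so that the subgroups in 7.2 are defined. Say whether the Appendix O module is used.
- **Section 7.2, primary comparison:** prespecify site and baseline CDRS-R in the active-versus-sham analyses: ANCOVA for CDRS-R change, and the same two terms in the logistic model, noting that its odds ratio is then conditional on them.
- **Section 7.2, sensitivity analyses:** list the covariates in advance in place of choosing them from the baseline table. The table itself can stay as description.

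The cost is about one degree of freedom per added term, plus list set-up and SAP wording. No further subjects, visits or data are needed.

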5.3 Preparation and Administration of Investigational Device

Motor Threshold Determination Procedure – per NeuroStar User Manual:

1. To determine motor threshold, move the coil down to the patient's head such that the coil is at the vertex and the SenStar tab is aligned above the top of the ear.
2. Move the A/P bar forward until it aligns with the side of the coil.
3. Align the center line on the coil with the 0 degree mark on the coil angle indicator and move back the A/P bar.
4. Once contact and position have been established, ask the subject to enact the hitchhiker position: arm bent 90 degrees at the elbow, fist held loosely, thumb extended outwards.
5. Begin stimulation and focus on any movement of the thumb.
6. Gradually increase the MT level from 0.68 to 1.10 until thumb or concordant finger movement is seen.
7. Once movement is established, begin searching for the motor hotspot. Move the coil around in a grid like pattern, adjusting the MT level as needed. Continue this search until you find a location and power level setting that elicits exactly 5 thumb twitches out of 10 consecutive pulses.
8. Once the motor hotspot has been determined, move the A/P bar forward until it, once again, aligns with the side of the coil.
9. Use the touch screen interface to record the A/P position, Coil Angle, SOA position, and Power Level.
10. Finally, press the Found MT button.

Subjects in Phase I randomized to active treatments will receive treatment parameters that have been safely and feasibly utilized in adult randomized, controlled trials [7, 8] and the 2011 Wall et al. open-label trial in adolescents.[1] Stimulation will occur at a maximum of 120% magnetic field intensity relative to the subject's resting motor threshold (MT), at 10 pulses per second (10 Hz) for 4 seconds, with an intertrain interval of 26 seconds. During the treatment, intensity can be reduced, as needed, to 80% for tolerability. Upward titration with goal of return to maximum intensity (not to exceed 120% MT) will occur as tolerated by each participant. This is not expected to impact treatment response but may make the treatment experience more comfortable for the participating adolescents. Treatment sessions will last for 37.5 minutes (75 trains) to provide a total of 3,000 pulses per treatment session. A total of 30 treatments will be completed within 6-8 weeks of treatment initiation.

Subjects in Phase I randomized to sham treatments will have identical schedules, systematic assessments, and a treatment approach to active treatment. Neither the adolescents nor the investigators will know whether the treatment is active or sham in nature. The sham coil will be identical in its appearance to the active coil. Furthermore, Neuronetics, Inc. has created an acoustic matching profile that renders the "sound" of the treatments virtually indistinguishable to subjects or researchers. The acoustic signal creates a painless percussive sensation that will be felt by the subject and will assist in simulating the active condition.

Subjects in Acute Treatment (Arm 1) of Phase II will receive treatment that is identical in schedule and parameters to that of Phase I with the exception that the known-active therapy coil will be used for all treatments. A total of 30 treatments will be completed within 6-8 weeks.

Subjects in Maintenance Treatment (Arm 2) of Phase II will undergo 52 weeks of maintenance rTMS treatment. The treatment parameters will be identical to those in Phase I except for the frequency of visits (biweekly) instead of daily. Clinical assessments will be offered monthly throughout the duration of the maintenance phase.

5.4 Subject Compliance Monitoring

During Phase I of the trial, subjects will complete 30 treatments within a 6- to 8-week timeframe. This schedule allows for the missing and/or rescheduling of up to 10 treatments over this timeframe. Subjects who are unable to comply with this schedule may be withdrawn from the investigational treatment portion of the study but will be offered ongoing mood, cognitive, safety, and imaging assessments as outlined in the study timeline (Table 4).

During Phase II of the trial, the Non-Responder Cohort from Phase I will receive acute rTMS treatment according to the schedule in Phase I. They will likewise be expected to complete 30 treatments within 6 to 8 weeks (Table 5).

The Responder Cohort from Phase I will receive maintenance treatments in Phase II with a biweekly treatment schedule over the course of 52 weeks (26 treatments). A total of 8 sessions can be missed over the course of 52 weeks (Table 6). More than 8 missed sessions will result in subject withdrawal from the study.

